9.5 Primary Endpoint Analysis

The primary endpoint is the performance measure of P30 for transdermal-derived GFR with respect to the plasma-derived indexed GFR, with a 95% confidence interval. The performance goal is 85%. Success for the study will be that the lower limit of the 95% CI is greater than 85%.

Prior data demonstrated for a P30 true value of 0.95, alpha of 0.025, performance goal of 85%, power of 90%, the one-sided exact binomial test yields a sample size of 102. As the reusable sensor is new, an adaptive trial design will be employed.

A Run-in Cohort of up to 30 evaluable subjects will be enrolled to test monitor algorithm settings with the TGFR reusable sensor with disposable adhesive ring. Additional run-in subjects may be enrolled at new clinical sites to ensure protocol compliance. Run-in subject data will be considered tuning data. The following will be enrolled into the run-in cohort:

- At least 5 subjects will be enrolled in Stratum 2
- At least 4 subjects in each of the FSS I-II; III-IV and V-VI
- Validation Cohort 1 (approximately 20 evaluable subjects) will be used to confirm final algorithm selection. Validation Cohort 1 subject data will be considered tuning data.
- Validation Cohort 2 (approximately 75 evaluable subjects) will be analysed in an interim analysis to compare results against the primary endpoint specification. At that time, the primary endpoint null hypothesis will be tested using an exact binomial test at a one-sided nominal alpha level of 0.0150 using the method of Pocock for a two-stage design with the interim analysis performed based on the first 53.57% of the planned number of subjects. At the final analysis, the primary endpoint null hypothesis will also be tested at a one-sided nominal alpha level of 0.0150. This will control the overall Type I error rate at the one-sided 0.025 level.

- If the primary endpoint has been achieved, the study will be terminated. If not, the trial will be continued.
- Validation Cohort 3 (approximately 65 evaluable subjects) will be enrolled in the event the interim analysis did not meet the primary outcome measure. Final analysis will be of the 140 evaluable subjects.

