	7.5	Outcome o	f the Event	24
	7.6	Evaluation	of Device Malfunctions	24
8	C	GENERAL STA	TISTICAL CONSIDERATIONS	25
	8.1	Analysis Se	ts	25
	8.2	Sample Size	e Determination	25
	8.3	Pooling Da	ta Across Sites	26
	8.4	Handling o	f Missing Data	27
	8.5	Statistical S	Software	27
	8.6	Descriptive	Statistics	27
	8.7	Statistical S	Significance	27
	8.8	Subject Dis	position	27
	8.9	Analysis		28
9	(CHANGES FRO	OM PLANNED ANALYSES	28
1(0 9	SUBJECT LISTI	NGS	28
1:	1 7	TABLES		29

Statistical Analysis Plan		Page 6 of 29
MediBeacon Inc.	An Open Label, Multi-Center, Safety and Pharmacokinetic Bridging Study of MB-102 (Relmapirazin) and the Use of the MediBeacon [®] Transdermal GFR Measurement System using the TGFR Reusable Sensor with Disposable Adhesive Ring in Normal and Renal Compromised Subjects for the Evaluation of Kidney Function	Ver 4.0

1 Introduction

This statistical analysis plan (SAP) describes the planned statistical methods to be used during the reporting and analysis of data collected under the Clinical Investigation Protocol, "An Open Label, Multi-Center, Safety and Pharmacokinetic Bridging Study of MB-102 (Relmapirazin) and the Use of the MediBeacon® Transdermal GFR Measurement System using the TGFR Reusable Sensor with Disposable Adhesive Ring in Normal and Renal Compromised Subjects for the Evaluation of Kidney Function". This SAP should be read in conjunction with the study Clinical Investigation Plan and associated case report forms (CRFs). This version of the analysis plan has been developed with respect to the Study Protocol Version 5.1. Any revisions to the protocol or CRFs that impact the planned analyses may require updates to the SAP. If there are any discrepancies between the SAP and the protocol, the SAP will prevail.

2 Study Design

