3.3 Safety Evaluation

Safety of MB-102 will be evaluated through treatment emergent adverse events (TEAEs), where treatment emergence is defined with respect to the first administration of MB-102.

Safety of the MediBeacon® Transdermal GFR Measurement System will be evaluated through TEAEs, where treatment emergence is defined with respect to the start time of device use. Additional safety variables include physical examinations, clinical laboratory assessments, ECGs, and concomitant medication use. All clinically significant findings in physical examinations, clinical laboratory assessments and ECGs will be reported as an AE or as medical history (if observations are noted prior to dose administration).

Statistical Analysis Plan		Page 12 of 29
MediBeacon Inc.	An Open Label, Multi-Center, Safety and Pharmacokinetic Bridging Study of MB-102 (Relmapirazin) and the Use of the MediBeacon [®] Transdermal GFR Measurement System using the TGFR Reusable Sensor with Disposable Adhesive Ring in Normal and Renal Compromised Subjects for the Evaluation of Kidney Function	Ver 4.0

4 Analysis of Primary Endpoint

The primary endpoint is the performance measure of P30 for transdermal-derived GFR with respect to the plasma-derived indexed GFR, with a 95% confidence interval. The performance goal is 85%. Success for the study will be that the lower limit of the 95% CI is greater than 85%.

The primary endpoint will be calculated for subjects enrolled into the Validation 2 and 3 (if applicable) cohorts only. The Run-in cohort and Validation 1 cohort enrollment were performed to provide final tuning data and used for software updates.

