8.2 Sample Size Determination

The One-Sample Proportion Test is used to calculate the sample size. The required sample size was calculated assuming the true proportion is 0.95, the test is one-sided exact binomial, $\alpha = 0.025$, and the power is $1 - \beta = 0.90$. The P30 sample size calculation yields 102 subjects. However, to remain consistent with the previous sample size from the pivotal study (protocol 100-003) for the TGFR, the study will enroll 140 evaluable subjects.

Statistical Analysis Plan		Page 26 of 29
MediBeacon Inc.	An Open Label, Multi-Center, Safety and Pharmacokinetic Bridging Study of MB-102 (Relmapirazin) and the Use of the MediBeacon [®] Transdermal GFR Measurement System using the TGFR Reusable Sensor with Disposable Adhesive Ring in Normal and Renal Compromised Subjects for the Evaluation of Kidney Function	Ver 4.0

An adaptive trial design will be employed for the reusable sensor as follows:

- 1. Run-in cohort of up to 30 evaluable subjects will commence the study. Additional Run-in subjects may be enrolled at new clinical sites to ensure protocol compliance. Run-in subject data will be considered tuning data.
- 2. Validation Cohort 1 (approximately 20 evaluable subjects) will be used to confirm final algorithm selection. Validation Cohort 1 subject data will be considered tuning data.
- 3. Validation Cohort 2 (approximately 75 evaluable subjects) will be analyzed in an interim analysis to compare results against the primary endpoint specification. At that time, the primary endpoint null hypothesis will be tested using an exact binomial test at a one-sided nominal alpha level of 0.0150 using the method of Pocock for a two-stage design with the interim analysis performed based on the first 53.57% of the planned number of subjects. At the final analysis, the primary endpoint null hypothesis will also be tested at a one-sided nominal alpha level of 0.0150. This will control the overall Type I error rate at the one-sided 0.025 level.
- 4. If the primary endpoint has been achieved, the study will be terminated. If not, the trial will be continued.
- 5. Validation Cohort 3 (approximately 65 evaluable subjects) will be enrolled in the event the interim analysis did not meet the primary outcome measure. Final analysis will be of the 140 evaluable subjects.

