8.6 Descriptive Statistics

Continuous data will be summarized with the number of evaluable observations, mean, standard deviation, median, minimum, and maximum. Categorical variables will be summarized with frequency counts and percentages. Summaries will be based on observed data (i.e., no missing data will be imputed). Confidence intervals may be presented, where appropriate, using the t-distribution for continuous data and Clopper-Pearson Exact method for categorical variables.

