8.7 Statistical Significance

Unless otherwise specified, hypothesis testing will be performed at the two-sided 0.05 significance level and one-sided 0.025 significance level. Nominal p-values will be rounded to four decimal places. If a nominal p-value is less than 0.0001 it will be reported as "<0.0001". In the event of multiple testing the overall type I error becomes inflated. There are several strategies to correct the alpha level when performing multiple tests. In this study, to control the inflation of overall type I error, the Benjamini-Hochberg method will be applied.

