8.9 Analysis

After the run-in cohort, the study will include up to 140 evaluable subjects. After 75 evaluable subjects have completed the study, an interim analysis will be conducted. If the primary endpoint has been reached, the study will be terminated. If the primary endpoint has not been completed, the study will continue until 140 evaluable subjects have completed the study.

9 Changes from Planned Analyses

Any changes to planned statistical analyses determined necessary prior to performing the analyses will be documented in an amended Statistical Analysis Plan and approved prior to the analysis when possible. Any other deviations or changes from the planned analyses deemed necessary due to violation of critical underlying statistical assumptions, data characteristics, or missing data will be clearly described in the clinical study report with justification and rationale.

10 Subject Listings

Subject listings will be provided for the primary endpoint. Listings will also be provided for adverse events.

All plasma concentrations will be provided in listings by subject and time point. Any blood measurements obtained outside of a ± 2 minute window around the scheduled time point for up through 90 minutes, and a ± 5 minute window for the remaining sampled collected will be identified as protocol deviations. Additionally, pharmacokinetic parameters will be provided in listings sorted by subject.

Concomitant medications administered within 3 days prior to MB-102 dose administration and through the follow-up study visit will be listed. Medications will be coded using the World Health Organization (WHO) drug dictionary. Data will be provided in one or more subject data listings. Concomitant non-drug therapies will be listed. ECG data will be listed.

Statistical Analysis Plan		Page 29 of 29
MediBeacon Inc.	An Open Label, Multi-Center, Safety and Pharmacokinetic Bridging Study of MB-102 (Relmapirazin) and the Use of the MediBeacon [®] Transdermal GFR Measurement System using the TGFR Reusable Sensor with Disposable Adhesive Ring in Normal and Renal Compromised Subjects for the Evaluation of Kidney Function	Ver 4.0

11 Tables

Table 1 Clinical Laboratory Analytes

Chemistry Panel	Hematology	Other required lab tests

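### The success sentence (95% CI lower limit above 85%) was not aligned with the exact one-sided 0.0150 test set for both looks, so 70/75 and 128/140 pass one rule and fail the other

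*SAP*

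**What the plan says.** Two decision rules for the same endpoint stand in the current text.

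- **Success sentence.** SAP 3.1, SAP 4, protocol 9.5 and the protocol synopsis (under both the primary endpoint and the statistical analyses) say: "Success for the study will be that the lower limit of the 95% CI is greater than 85" percent. None of these sentences adjusts for the interim look.
- **Two-look test.** SAP 8.2, with matching text in protocol 9.5, says of the interim: "At that time, the primary endpoint null hypothesis will be tested using an exact binomial test at a one-sided nominal alpha level of 0.0150". It continues: "At the final analysis, the primary endpoint null hypothesis will also be tested at a one-sided nominal alpha level of 0.0150". Both documents attach the error claim to this test: "This will control the overall Type I error rate at the one-sided 0.025 level".

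Three other provisions bear on how the two fit together.

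- SAP 8.7 sets a default level: "Unless otherwise specified, hypothesis testing will be performed at the two-sided 0.05 significance level and one-sided 0.025 significance level".
- SAP 8.9 sets the stopping trigger without naming a rule: "If the primary endpoint has been reached, the study will be terminated".
- SAP 8.6 mentions an interval method only permissively: "Confidence intervals may be presented, where appropriate, using the t-distribution for continuous data and Clopper-Pearson Exact method for categorical variables".

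**The concern.** A two-sided 95% interval with exact limits has a lower bound above 85% exactly when the one-sided exact test rejects at 0.025. The success sentence is therefore a looser rule than the prescribed 0.0150 test. No sentence says that it yields to the test or that both conditions apply.

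The ordinary tie-breakers do not settle this. The SAP's precedence clause ("If there are any discrepancies between the SAP and the protocol, the SAP will prevail") cannot help, because both rules are in the SAP. The default in SAP 8.7 makes clear that 0.0150 is the level of the test, but it governs test levels and does not redefine the success sentence. The interim stop depends on the primary endpoint having been met, and the sections that define that endpoint (SAP 3.1 and 4) give only the 95% interval. In the SAP, the 0.0150 level appears only under sample size.

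At stake are the stopping decision at the interim, the study conclusion at the end, and the overall 0.025 claim, which holds for the test but not for every reading of the success sentence. The study is open-label and single-arm and turns on one count, so the choice of rule should not be left open until that count is known.

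**Working it through.** **Inputs.** Null P30 = 0.85 (the performance goal), planning P30 = 0.95, interim n = 75, final n = 140, nominal one-sided level 0.0150 at each look, overall level 0.025 (all SAP 8.2 or protocol 9.5 and 9.7). Clopper-Pearson limits for the success sentence are an assumption, since SAP 8.6 does not name a method for the primary endpoint.

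**The plan's own figures.** At n = 102 the exact test at 0.025 rejects at 94 or more: P(X ≥ 94 | 102, 0.85) = 0.0231 and P(X ≥ 94 | 102, 0.95) = 0.930. At n = 101 power is 0.867, and from 102 onwards it stays at or above 90%. The stated 102 is reproduced. The Pocock level at 75/140 = 53.57% information computes to 0.0149 (z = 2.172), in effect the stated 0.0150; the cut-offs below do not change.

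**Step 1: cut-offs at each look.** The exact p-value is P(X ≥ x | n, 0.85). The lower limit is the α quantile of Beta(x, n − x + 1), with α = 0.025 for a 95% interval and 0.015 for a 97% interval.

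| Result | Exact one-sided p | 95% lower limit | 97% lower limit | 95% CI sentence | 0.0150 test |
|---|---|---|---|---|---|
| 69/75 | 0.0544 | 0.8340 | 0.8241 | fails | fails |
| **70/75** | 0.0234 | 0.8512 | 0.8417 | **passes** | **fails** |
| 71/75 | 0.0084 | 0.8690 | 0.8599 | passes | passes |
| 127/140 | 0.0322 | 0.8465 | 0.8396 | fails | fails |
| **128/140** | 0.0170 | 0.8551 | 0.8484 | **passes** | **fails** |
| 129/140 | 0.0083 | 0.8638 | 0.8572 | passes | passes |

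The 97% limit agrees with the 0.0150 test in every row.

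**Step 2: overall type I error.** For cut-offs r1 at 75 and r2 at 140,

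P(success) = P(X1 ≥ r1) + Σ over x < r1 of P(X1 = x) · P(X2 ≥ r2 − x), with X1 ~ Bin(75, p) and X2 ~ Bin(65, p).

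At p = 0.85:

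- 0.0150 test at both looks (71, 129): 0.0084 + 0.0061 = 0.0145. Requiring both rules gives the same result.
- 0.0150 at interim, 95% CI at final (71, 128): 0.0084 + 0.0137 = 0.0221.
- 95% CI at both looks (70, 128): 0.0234 + 0.0104 = 0.0338.

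**Step 3: power, same formula.**

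| True P30 | (71, 129) | (71, 128) | (70, 128) |
|---|---|---|---|
| 0.95 | 0.956 | 0.978 | 0.980 |
| 0.93 | 0.744 | 0.826 | 0.841 |
| 0.92 | 0.582 | 0.684 | 0.708 |

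**Step 4: how likely the disputed counts are.** P(X = 70 | 75, 0.95) = 0.149. The chance of ending at 128/140 after not passing 0.0150 at the interim is 2.2%, 8.2% and 10.2% at P30 = 0.95, 0.93 and 0.92.

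**Step 5: other interim sizes.** The cohort is approximately 75, so n = 70 to 80 is taken as an assumed range, with final n = 140 and cut-offs recomputed at each n.

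- 0.0150 at both looks: 0.0119 to 0.0201, always below 0.025.
- 0.0150, then 95% CI: 0.0199 to 0.0272, above 0.025 at n = 70 (0.0272), 71 (0.0259) and 80 (0.0259).
- 95% CI at both looks: 0.0229 to 0.0338.

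At n = 70 to 74 and at 80 the two rules share the same interim cut-off, so there the last two readings coincide.

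**Step 6: interval method.** Cut-offs for the success sentence (75; 140): Clopper-Pearson and Wilson 70; 128. Agresti-Coull 71; 128. Jeffreys 70; 127. Wald 69; 126.

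**The case against.** The strongest reply is that the decision rule is already prespecified. SAP 8.2 and protocol 9.5 name the test, the level, both looks and the purpose, and SAP 8.7 gives way where another level is specified. In protocol 9.5 the success sentence and the test stand in one section, so the specific test can be read as carrying out the general sentence. Anyone who follows it controls the error, at no more than 0.0201 for any interim size from 70 to 80. The 0.0338 figure arises only if an explicit instruction is disregarded at both looks. This stands as regards weight: the test itself is sound. It does not supply the missing sentence giving the test precedence.

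The other points also limit the size of the problem.

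- **The rules are nested.** With exact limits, any result that passes the test passes the success sentence, and the gap at the planned sizes is one count per look.
- **Failing at 70/75 is not study failure.** The trial goes on to Validation Cohort 3. The chance of 70/75 followed by a total below 129/140 is 0.64%, 3.0% and 4.3% at P30 = 0.95, 0.93 and 0.92. The 14.9% therefore describes a disputed stop, not a changed conclusion.
- **The dispute depends on n.** The interim cut-offs coincide at six of the eleven sizes from 70 to 80, and the final cut-offs coincide at 142 and 143.
- **The interim dispute depends on the interval method.** Agresti-Coull removes it. The dispute at 128/140 remains under every method listed.

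**Conclusion.** The concern holds. The plan contains a sound two-look test and, beside it, a success sentence that was not brought into line. At the planned sizes the two disagree at 70/75 on stopping and at 128/140 on the conclusion.

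The plan's 0.025 claim is true of the 0.0150 test (0.0145). It is also true, at 75 and 140, if the 95% interval replaces the test only at the end (0.0221), though not at every nearby interim size. It is false if the success sentence is applied as written at both looks (0.0338).

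These figures assume Clopper-Pearson limits and looks at exactly 75 and 140. This should be fixed, but it is a defect of definition and not of the underlying design. Confidence is high.

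**What to change.** In the protocol synopsis and 9.5, and in SAP 3.1, 4 and 8.9, define success at each look as rejection of P30 ≤ 0.85 by the exact one-sided binomial test at 0.0150. The equivalent interval statement is that the lower limit of the two-sided 97% Clopper-Pearson interval exceeds 85%. State that the cut-offs are computed from the actual evaluable number at each look; they are 71/75 and 129/140 if the planned sizes are met. Keep the 95% interval as a descriptive summary and name its method. Make the change before the counts are known.

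The cost is wording only. Nothing changes relative to the test already in SAP 8.2 and protocol 9.5. Relative to the 95% CI sentence, the cut-off rises by one success at each look at the planned sizes. Power at P30 = 0.95 is then 95.6%, instead of 98.0% with the 95% interval at both looks or 97.8% with it only at the final look. That is still above the 90% used for sizing.

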4.1 Subgroup and Stratified Analysis

For the primary effectiveness endpoints, all data will be included in the primary analysis. To examine the consistent device performance, two sub-group analyses will be performed. The first sub-group analysis will be nGFR vs tGFR for eGFR > 70 mL/min/1.73 m², and then for eGFR < 70 mL/min/1.73 m². The second sub-group analysis will be nGFR vs tGFR for FSS I-III, and then for FSS IV-VI.

FSS will be generated based on Mexameter melanin measurements collected on the dosing day instead of using the subjective screening categorization. The mean of the melanin will be calculated and the FSS applied per the Mexameter manual (below):

- **FSS I: Nordic/Celtic skin:** extremely white skin, often red hair and freckles, never tan, always sunburns, **average melanin content:** 0 100
- **FSS II: Light Caucasians:** very light skin, often blond, tans with difficulty and sunburns quickly, **average melanin content:** 100 150
- **FSS III: European mixed type/ very fair Asian skin:** light skin, dark blond to brown hair, tans sometimes, sunburns sometimes, **average melanin content:** 150 250
- FSS IV: Mediterranean/fair Asian skin: dark hair, tans well and sunburns rarely, average melanin content: 250 350
- FSS V: Dark skin: e.g. dark Asians, tans very well and sunburns almost never, average melanin content: 350-450
- FSS VI: Black skin: Immediately tans and never sunburns, average melanin content: 450 999

Note that the 30 evaluable subjects used for the run-in cohort and the 20 subjects enrolled into Validation Cohort 1 will not be included in the primary endpoint analysis as these data are considered Tuning Data.

Statistical Analysis Plan		Page 13 of 29
MediBeacon Inc.	An Open Label, Multi-Center, Safety and Pharmacokinetic Bridging Study of MB-102 (Relmapirazin) and the Use of the MediBeacon [®] Transdermal GFR Measurement System using the TGFR Reusable Sensor with Disposable Adhesive Ring in Normal and Renal Compromised Subjects for the Evaluation of Kidney Function	Ver 4.0

5 Pharmacokinetic Analysis

Pharmacokinetic blood samples will be collected at the time points noted in **Section 2.4.** Single-dose pharmacokinetic parameters for MB-102 will be calculated using compartmental analysis methods.

5.1 Compartmental Pharmacokinetic Data Analysis

A compartmental pharmacokinetic analysis will be performed separately using each subject's plasma concentration-time profile. Based on prior data, it is expected that a two compartmental model will provide an adequate fit using Phoenix WinNonlin (Certara, Version 8.1 or higher). Model PK parameters for each subject will be reported.

Parameter	Units ^a	Definition
AUC	h*ng/mL	area under the plasma concentration-time curve, calculated as AUC=A/ α + B/ β
C_{max}	ng/mL	maximum plasma concentration, calculated as Dose/V
$t_{1/2\alpha}$	h	half-life associated with distribution phase
$t_{1/2\beta}$	h	half-life associated with elimination phase
$t_{1/2}$	h	elimination half-life from central compartment
CL	L/h	systemic clearance
V	L	total volume of distribution
V1	L	volume of distribution for central compartment
V2	L	volume of distribution for peripheral compartment

5.2 Calculation of nGFR *nGFR_{BSA}* – calculation of indexing to body surface area (BSA):

The GFR for each subject is obtained from the two-compartment pharmacokinetic model.

Statistical Analysis Plan		Page 14 of 29
MediBeacon Inc.	An Open Label, Multi-Center, Safety and Pharmacokinetic Bridging Study of MB-102 (Relmapirazin) and the Use of the MediBeacon [®] Transdermal GFR Measurement System using the TGFR Reusable Sensor with Disposable Adhesive Ring in Normal and Renal Compromised Subjects for the Evaluation of Kidney Function	Ver 4.0

BSA in units of m² is calculated for each subject from their height and weight using the formula¹:

$$BSA = 0.007184 * height_{cm}^{0.725} * weight_{kg}^{0.425}$$

$$nGFR_{BSA} = \frac{GFR (mL/min)}{\frac{BSA (m^2)}{1.73}} = \frac{GFR (mL/min)}{BSA (m^2)} * 1.73$$
 (Eqn. 1)

Note that in clinical practice GFR indexed to BSA (nGFR_{BSA}) is reported as "mL/min/1.73 m²".

$nGFR_{Vd}$ – calculation of indexing to volume of distribution (V_d):

The GFR and volume of distribution (V_d) for each subject is obtained from the two-compartment pharmacokinetic model.

$$nGFR_{Vd} = \frac{GFR(mL/min)}{\frac{V_d(L)}{13.3}} = \frac{GFR(mL/min)}{V_d(L)} * 13.3$$
 (Eqn. 2)

The standard value of 13.3 L for V_d was derived from our earlier clinical studies by computing the mean BSA across all subjects and computing the ratio of 1.73 m² to the mean BSA. This ratio was then multiplied by the mean V_d across all subjects to obtain the standard value of 13.3 L.

Note: Dosing day height and dosing day weight will be used for BSA / BMI calculations, however in the event dosing day weight or height is unavailable, screening day weight or height may be used.

¹ DuBois D, DuBois EF. A formula to estimate the approximate surface area if height and weight be known. Arch Intern Medicine. 1916; 17:863-71.

Statistical Analysis Plan		Page 15 of 29
MediBeacon Inc.	An Open Label, Multi-Center, Safety and Pharmacokinetic Bridging Study of MB-102 (Relmapirazin) and the Use of the MediBeacon [®] Transdermal GFR Measurement System using the TGFR Reusable Sensor with Disposable Adhesive Ring in Normal and Renal Compromised Subjects for the Evaluation of Kidney Function	Ver 4.0

5.3 Criteria for Handling Concentration Below the Limit of Quantification or Missing Concentrations for Pharmacokinetic Analysis

Plasma concentrations below the limit of quantification (BLQ) will be assigned a value of 0 before the first measurable concentration and thereafter BLQ concentrations will be treated as missing. The following rules apply to the specific situations defined below:

- If an entire concentration-time profile is BLQ, it will be excluded from PK analysis.
- Where 2 or more consecutive concentrations are BLQ at the end of a profile, the profile will be deemed to have terminated and any further quantifiable concentrations will be set to missing for the calculation of the PK parameters, unless they are considered to be a true characteristic of the profile of the drug.
- If a predose plasma concentration is missing, it will be set to 0 by default within Phoenix WinNonlin.

